In this pilot study, 55 participants will be accepted from our referral sources in the department of Neurology and Physical Medicine. There will be 3 measurement periods before the training starts, separated by 2-10 days in order to establish a baseline walking speed. Following the lead-in period, each subject will attend eighteen 60-minute sessions (3 visits/week) over a 6-week period (or up to 8-weeks to allow for missed appointments) comprising the training period. Participants will undergo midpoint and discharge outcome measures during training, at sessions nine and eighteen, respectively. Subjects will then return for a final 3-month follow-up visit for further outcome measures. All study procedures will be administered or supervised by the research coordinator, study investigator, or a certified physical or occupational therapist. All visits will be conducted in either the robot suite at the Northwell Health Transitions Outpatient Rehabilitation Center, the robotics suite in the Clinical Research Center at the Feinstein, or at Long Island Pediatric Physical Therapy, which is the rehab office of [name], PT.

Lead-in Period

- Week 1, Visit 1 (approximately 60 minutes)
 - Clinical outcome measures
 - Medical screening
 - Consent
- Week 2 & 3, Visit 2 & 3 (approximately 60 minutes each)
 - Clinical outcome measures
 - Objective Gait Measures

Training Period

- Week 4-6 Visit 4-11 (approximately 1 hour)
 - Robotic training
- Week 6 Visit 12 (approximately 90 minutes)
 - Robotic training
 - Midpoint Outcome Measures
- Week 7-9 Visit 13-21 (approximately 1 hour)
 - Robotic training
- Week 10, Visit 22 (approximately 1 hour)
 - Discharge Clinical outcome measures
 - Discharge Objective Gait Measures

Final Visit

- Week 22, Visit 23 (approximately 60 minutes)
 - Follow Up clinical outcome measures
 - Follow Up Objective Gait Measures

Clinical Outcome Measures

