Stroke Impact Scale (SIS): The SIS is a valid and reliable index that assesses changes in impairments, disabilities and handicaps following a stroke and has internal consistency and established test-retest reliability [21, 22]. We have chosen the Stroke Impact Scale (SIS) Version 3.0 to measure physical abilities, as well as other dimensions that contribute to quality of life and participation in everyday life. This is a 59-item self-reported questionnaire that asks persons with stroke to rate perceived problems in eight domains using a 5-point scale: strength, hand function, mobility, activities of daily living, emotion, memory, communication and social participation. This self-report assessment is unique in that it addresses motor impairments of the paretic limbs in addition to other key variables that are important to patients and their caregivers. This assessment will not only offer data concerning perceived changes in motor abilities following involvement in the planned study, but will also help to identify other incidental changes in emotional status, memory and thinking, or activities of daily living following participation in robot training.

Activities-specific Balance Confidence Scale: The Activities-specific Confidence Scale is a valid and reliable 16 point self-report measure of an individual's confidence in performing ambulatory activities after stroke without falling [23].

Objective Gait Measures

Gait analysis measures for fast and comfortable pace will be recorded twice prior to the training period (baseline); measurements will be separated by 2-10 days to ensure reliability and stability of measures. Measures will be taken again at week ten (discharge) of the training program and once more three months following completion of training (follow up). Gait analysis will be performed at the Long Island Pediatric Physical Therapy, which is the rehab office of [name], PT.

Kinematic Measures will be taken with the Zeno Walkway, which is an electronic floor mat, containing a 16-level pressure sensing pad and circuitry inside a flat, linoleum surfaced walkway. The Kinematic measures will serve to objectively describe the geometry of movement, including step speed, length, power, center of oscillation, and step symmetry. These metrics are valid and reliable objective measures of changes in gait pattern [29-32].

STATISTICAL CONSIDERATION AND DATA ANALYSIS

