The primary outcome measure for a robotic trial of the lower extremity is the 10 Meter Walking Test, which is a widely used clinical metric of functional ambulation status post-stroke. Gait speed is the critical measure that tracks functional independence [17]. We will use the accepted post-stroke definitions of impaired ambulation: with severe impairment defined by gait speeds below 0.4m/s, moderate impairment as 0.4-0.8m/s (limited community ambulation ambulation), mild impairment as 0.8-1.2m/s (community ambulation), and functional independence as 1.2-1.4m/s or greater. The reliability and validity of this scale is accepted by clinical researchers as well as clinicians [18, 19].

Secondary outcome measures will include the 6 minute walk test, the Berg Balance Scale, objective gait measures, the Stroke Impact Scale, and the Activities-specific Balance Confidence Scale, which together

provide valid and reliable measures of aerobic capacity for ambulation, functional balance, objective measures of gait pattern, and subjective impression of mobility impairment after stroke.

The clinical evaluations will be administered at baseline, 9 (midpoint) and 18 (discharge) sessions, and 3 months after completion. The paired t-test (and nonparametric Wilcoxon signed-rank test) will be used to evaluate mean score changes for different interventions (i.e., within-group comparisons over time). The independent two-sample t-test (and nonparametric Wilcoxon rank-sum test) will be used to evaluate mean score differences between interventions immediately after treatment and after 3 months. Similar analyses will be repeated for the secondary measures. In our previous studies, randomization has led to comparable groups (baseline) and we expect the same here. We will also perform a repeated measures analysis of variance (RMANOVA) with group as a between-subject factor, and time as a within-subject factor. Because we have repeated measures over time and have two groups to compare at a time, this analysis will allow us to assess potential treatment-by-time interactions more accurately. We will also perform an analysis of covariance (ANCOVA) with treatment protocol as a between-subject factor.

POWER ANALYSIS

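### Nothing in the protocol keeps a participant's trainer from running that participant's primary walking test, and no instrument-based supporting analysis of the primary result is named

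*Combined protocol and SAP*

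**What the plan says.** The Visit Schedule section covers staffing in one sentence: "All study procedures will be administered or supervised by the research coordinator, study investigator, or a certified physical or occupational therapist". It makes no distinction between delivering robotic training and measuring outcomes. No section mentions masking, an independent assessor, or a rule that trainer and tester differ.

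The Statistical Consideration section states: "The primary outcome measure for a robotic trial of the lower extremity is the 10 Meter Walking Test". Neither that section nor Clinical Outcome Measures says who times the test, how it is timed, at what pace, or with what instructions to the participant.

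The Objective Gait Measures section adds an instrumented measurement: "Kinematic Measures will be taken with the Zeno Walkway, which is an electronic floor mat". Its purpose is to "objectively describe the geometry of movement, including step speed, length, power, center of oscillation, and step symmetry". It is recorded at fast and comfortable pace, twice before training, at discharge and three months after training. This section lists no midpoint recording. In the analysis plan these data are secondary: "Secondary outcome measures will include the 6 minute walk test, the Berg Balance Scale, objective gait measures". The plan then says "Similar analyses will be repeated for the secondary measures". It plans no comparison of walkway speed with the 10 Meter Walking Test and does not say what follows if the two disagree.

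**The concern.** The Specific Aims and Visit Schedule describe all 55 participants receiving the training, so the comparison the design supports is each participant's change from before to after. Under that design every tester knows the participant has been trained and knows which visit it is. If testers stop the watch slightly early, or encourage more, after training than before, the shift goes straight into the estimated change, with no control arm to cancel it.

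The Statistical Consideration section also refers to randomization and to comparing two groups. No second arm is described elsewhere, and these statements must be reconciled with the aims.

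Two features add weight. The Conflict of Interest section says two co-PIs are co-inventors of the device. The Power Analysis section says the pilot will inform the power calculation for a later comparison with standard training. If the observed change were used as the planning effect, an inflated value would make that trial too small.

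**Working it through.** The plan has no figure of its own to reproduce: it states a sample size but no alpha, power, effect size or SD. What follows is an illustration.

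**Inputs from the documents.** Target sample size is 55. Dropout is under 5% for treatment and 10% for all measurements (Power Analysis). Completers are therefore 55 × 0.95 = 52.25, taken as 52, or 55 × 0.90 = 49.5, taken as 49. The within-group test is a paired t-test (Statistical Consideration).

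**Assumptions not in the documents.** A timed distance of 10 m; two-sided alpha of 0.05; SD of change s of 0.10, 0.15 or 0.20 m/s; a true change of zero; and a systematic post-training shift b.

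**Step 1: what a timing shift does to speed.** If the true time is t = 10/v and the watch is stopped e seconds early, the error is 10/(t − e) − v. Take v = 0.6 m/s, the middle of the protocol's moderate band of 0.4-0.8 m/s, so t = 16.67 s:

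- e = 0.2 s: 10/16.47 − 0.6 = 0.007 m/s
- e = 0.5 s: 10/16.17 − 0.6 = 0.019 m/s
- e = 1.0 s: 10/15.67 − 0.6 = 0.038 m/s

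The same 0.5 s adds 0.008 m/s at 0.4 m/s and 0.033 m/s at 0.8 m/s, so the effect grows with walking speed. Only a consistent difference between pre- and post-training tests matters. Random timing error does not shift the mean.

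**Step 2: what that shift does to the test.** The noncentrality parameter is b√n/s, and the rejection rate is the probability that a noncentral t on n − 1 degrees of freedom falls outside the two-sided 5% limits. For n = 52, s = 0.15 and b = 0.02, the standard error is 0.15/√52 = 0.0208, the noncentrality is 0.02/0.0208 = 0.96, the limit is ±2.008, and the rejection rate is 15.7%.

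| Bias (m/s) | n = 52: SD 0.10 / 0.15 / 0.20 | n = 49: SD 0.10 / 0.15 / 0.20 |
|---|---|---|
| 0.01 | 11% / 8% / 6% | 11% / 7% / 6% |
| 0.02 | 29% / 16% / 11% | 28% / 15% / 11% |
| 0.04 | 81% / 47% / 29% | 78% / 45% / 28% |

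The nominal rate is 5%. The number of completers hardly matters; the size of the bias and the SD do.

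**Step 3: where the roles could overlap.** The visit list puts midpoint measures in Visit 12, which is also a training session, so the trainer is the obvious person to test there. Discharge is less clear. The visit list gives it a separate Visit 22 with no training, while the text above that list places it at session eighteen and the Schedule of Events places it at Visit 21.

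**The case against.** The strongest reply is that the staffing sentence is a statement of qualifications. It says who may administer or supervise procedures, not that one person does both jobs. The visit structure may already separate them. The visit list shows no training at Visits 2, 3, 22 and 23, where clinical and gait measures are taken together. The gait measures take place at a separate physical therapy office, while other study visits are generally at the recruiting institution. This stands in part: the baseline, discharge and follow-up walking tests may already be run away from the trainers. It does not settle the matter. The same office is also listed among the general visit locations, the timing of discharge is inconsistent, and no text makes the separation a requirement. A reader might infer that trainers do test their own participants, but the documents only leave that open.

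A reader might also infer that the walkway data go unused. They do not: they are a secondary outcome with analyses like those of the primary. What is missing is a named speed variable and pace, and a stated link to the primary result.

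Third, the remedies are partial. A walkway removes timing error but not encouragement or participant effort, and a different tester still knows the time point. This stands. Moreover, a separation rule applied only after baseline could make matters worse, because a change of tester would coincide with the change from before to after training. The rule must therefore cover baseline.

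Finally, the bias sizes are assumed, and the plan ties no decision rule to a 5% test. This also stands, and it limits how the figures may be used.

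**Conclusion.** The gap is real but limited. The plan allows the same staff member to train a participant and run that participant's primary test, describes no masking, and names no supporting analysis of the primary result. With everyone trained, a consistent tester effect would pass undiluted into the pre-post estimate.

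Its size is unknown. At a bias of 0.01 m/s the distortion is modest (6-11% against 5%); at 0.04 m/s it would be serious (29-81%). Those ranges rest on assumed SDs, an assumed alpha and an assumed one-directional bias. They do not show that the trial's result will be wrong.

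The documents do not support two further inferences. One is that the device's co-inventors will test participants: the protocol does not say so. It also says that two sub-investigators only assist in analysis and receive de-identified data, without saying whether these are the same people. The other is that the primary claim should stand only if the walkway shows a similar size of change. The documents supply no margin, no pace for the 10 Meter Walking Test and no matching definition of speed. The two measures also have different baselines, three visits against two, so they could disagree without any tester bias.

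**What to change.** 1. In the Visit Schedule, state that each participant's 10 Meter Walking Test is run by one listed staff member who does not deliver that participant's training. As far as possible this should be the same person at all baseline, midpoint, discharge and follow-up tests, using standard instructions. The cost is scheduling, mainly at Visit 12. No additional assessor is needed. The tester will still know the time point.

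2. In the Statistical Consideration section, name walkway-recorded speed, at the pace that matches the 10 Meter Walking Test, as the prespecified supporting analysis of the primary result. This requires stating the pace of the 10 Meter Walking Test and defining the walkway speed variable. Analyse change from the mean of the two pre-training walkway recordings to discharge and to three months. Set it beside the 10 Meter Walking Test change computed from the same baseline visits, and report any disagreement with the primary result. Do not make the primary claim conditional on agreement. The cost is one paragraph and one analysis of data already being collected. It addresses timing error only and, under the Objective Gait Measures section, cannot cover the midpoint.

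3. Reconcile the references to randomization and two groups with the aims. Also reconcile the timing of gait measures and of discharge across Visit Schedule, Clinical Outcome Measures, Objective Gait Measures and Schedule of Events.

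Overall this is a cheap improvement.

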With this protocol we now want to extend robot treatment to the lower limb. We want to initiate a pilot study using a device that has comparable safety features, identical motors that drive the movement of the manipulandum, and identical software programs that record the movement and drive the protocol to the devices that we have used successfully in robots for the upper extremity and in the protocols that have been approved by this IRB. This robot, however, fits around the foot and calf so that ankle flexion and extension can be trained; this device is called an ankle-bot. We want to treat the affected lower limb of patients with chronic stroke. Recent work shows that patients with chronic stroke who are exposed to ankle-bot treatment, first show that the ankle bot does not significantly alter a patient's gait on a treadmill [5]. Moreover, treated chronic stroke patients had decreased ankle stiffness [6] and demonstrated increased walking speed [7], a common measure of training effectiveness.

SPECIFIC AIMS

As part of our continuing effort to achieve a long-term goal of improving motor recovery after stroke, we will determine whether ankle-bot training improves gait speed in patients with chronic stroke. In this pilot study we will expose 55 patients consecutively referred from our referral sources in the department of neurology and physical medicine and rehabilitation to three one hour training periods per week on alternate days for 6 weeks. Prior to training, we will determine baseline gait speed across three measures separated by 2-10 day intervals. We will execute these measures again at the midpoint of training, at the end of training, and 3 months after training has ended.

PRELIMINARY STUDIES AND SIGNIFICANCE

Efforts using robotic devices to train the paretic arm of persons with acute or chronic impairments after stroke have consistently and significantly reduced the motor deficit without untoward side effects [1, 8-16]. Impairment reduction after this class of targeted training agrees with a prominent theme of brain injury recovery, namely, that activity-dependent plasticity underlies neurological recovery.

Recent work by others demonstrates that this ankle-bot is effective in improving gait speed and decreasing ankle stiffness in patients with chronic stroke [6, 7]. The added inertia and friction caused by wearing the ankle-bot device did not alter the gait during overground training or on a treadmill in patients with chronic stroke [5].

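### The planned between-group analyses cannot be estimated in a one-group study, and the within-group analysis that remains for gait speed names no deciding contrast

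*Combined protocol and SAP*

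**What the plan says.** **Design.** Specific Aims and Visit Schedule describe 55 consecutively referred patients, each given the same eighteen sessions. No control, second protocol, allocation ratio or randomization procedure is described. Power Analysis treats the study as input to a later comparison with standard training. The stated aim is inferential: "we will determine whether ankle-bot training improves gait speed in patients with chronic stroke".

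**Analysis** (Statistical Consideration and Data Analysis).
- Within group: "The paired t-test (and nonparametric Wilcoxon signed-rank test) will be used to evaluate mean score changes for different interventions".
- Between groups: the two-sample t-test and rank-sum test "will be used to evaluate mean score differences between interventions immediately after treatment and after 3 months".
- Balance: "In our previous studies, randomization has led to comparable groups (baseline) and we expect the same here".
- Repeated measures: "We will also perform a repeated measures analysis of variance (RMANOVA) with group as a between-subject factor, and time as a within-subject factor". The reason given begins: "Because we have repeated measures over time and have two groups to compare at a time".
- Covariance analysis: "We will also perform an analysis of covariance (ANCOVA) with treatment protocol as a between-subject factor".
- Timing: "The clinical evaluations will be administered at baseline, 9 (midpoint) and 18 (discharge) sessions, and 3 months after completion".

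**Baseline.** Visit Schedule plans three pre-training measurements, 2 to 10 days apart. Specific Aims says baseline gait speed will be determined over those three measurements, without saying how they are combined.

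**The concern.** The analysis section reads as if written for a randomized two-arm trial, while the design sections describe a single treated cohort. Once the parts that need a second group are set aside, the plan does not identify the comparison that answers the study's question. It leaves open whether midpoint, discharge or 3 months decides, and it gives no alpha or multiplicity rule.

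Two things are at stake. If the choice is not fixed before analysis, significance at any visit could be presented as improvement. The pilot is also meant to inform the power calculation for a later trial, and that calculation needs a defined change with a defined standard deviation.

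**Working it through.** **1. Plan's own figure.** The only planning number is the target of 55. No alpha, sidedness, power, effect or standard deviation accompanies it, so there is nothing to reproduce.

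**2. What can be estimated.** Let G be the number of groups and T the number of times. The design gives G = 1. Taking baseline as one level with midpoint, discharge and 3 months, T = 4.
- Group, or treatment protocol: G − 1 = 0 degrees of freedom.
- Group by time: (G − 1)(T − 1) = 0 degrees of freedom.
- Time: T − 1 = 3 degrees of freedom.

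The two-sample tests, the group and interaction terms and the ANCOVA treatment effect therefore do not exist in these data. The time effect, the paired t-test and the signed-rank test do.

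**3. Which contrast decides.** The timing sentence lists three post-baseline evaluations. The only test sentence that names times is the between-intervention one. It does not govern the paired tests, and it would still leave two times. The time effect is a global test and singles out no visit.

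**4. Illustrative error rate.** Assumptions, none of them in the documents: two-sided 5% paired t-tests, no true change, and improvement claimed if any time is significant in the favourable direction. I take n = 50 to 55, since 10% loss gives 55 × 0.90 = 49.5. With k times, P(false improvement) = 1 − P(every t statistic ≤ the upper 2.5% point).
- One time: 0.025.
- Independent change scores: 1 − 0.975² = 0.049 for two times and 1 − 0.975³ = 0.073 for three.
- Correlated change scores (100,000 simulated trials per setting; the ranges cover n = 50 and n = 55):

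| Change-score correlation | Two times | Three times |
|---|---|---|
| 0 | 0.050 | 0.072–0.073 |
| 0.5 | 0.045–0.046 | 0.062–0.064 |
| 0.8 | 0.039 | 0.050–0.051 |
| 0.95 | 0.032–0.033 | 0.038 |

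The correlation depends on the baseline rule. Suppose visits have equal variance σ² and equal correlation ρ, and the baseline is the mean of b measures. Each change then has variance σ²(1 − ρ)(1 + 1/b), and two changes have covariance σ²(1 − ρ)/b, so their correlation is (1/b)/(1 + 1/b) = 1/(b + 1). That is 0.5 for a single baseline and 0.25 for the mean of three. At 0.25 the three-time rate is about 6.8 to 6.9%.

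Letting the signed-rank test count as well moves the one-time rate only from 2.5% to 2.8–3.2%.

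**5. Why the baseline rule matters for the later trial.** Under the same assumptions the variance of change is 2σ²(1 − ρ) with one baseline measure and (4/3)σ²(1 − ρ) with the mean of three. The ratio is (4/3)/2 = 2/3. A standard deviation of change carried forward without its baseline rule is therefore ambiguous.

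**6. Where discharge falls.** The visit list puts training at Visits 4–11, 12 and 13–21, which is 8 + 1 + 9 = 18 sessions, so session 18 is Visit 21.
- Visit Schedule narrative and Statistical Consideration: discharge measures at session 18.
- Clinical Outcome Measures: week six of training.
- Visit list: discharge at Visit 22, week 10, with follow-up at Visit 23.
- Objective Gait Measures: week ten.
- Schedule of Events: discharge at Visit 21, with follow-up at Visit 22.

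Visit 22 is thus discharge in one place and the 3-month follow-up in another.

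**The case against.** The case for the plan has several parts, and much of it stands.
- **Not everything fails.** A reader might infer that nothing in the repeated-measures ANOVA can be run. The time effect can; only the group and interaction terms are lost. The gait-speed impairment bands in the same section could form a between-subject factor, but the planned comparisons are worded as comparing interventions and treatment protocols, so the bands do not rescue them.
- **Baseline is not ignored.** A reader might infer that no baseline approach is given. Specific Aims points towards pooling the three measurements. That makes the baseline underspecified rather than absent: mean, last and other combinations all fit the text.
- **The test choice is a small matter.** The paired t-test with a nonparametric companion is a natural reading, and the effect on the error rate is slight.
- **It is a pilot, and an amendment would settle it.** A reader might infer that the primary analysis can only be chosen after the data are seen. The documents do not force that, because an amendment before analysis would fix it. Reporting changes and standard deviations at every visit would also serve the power calculation. But the stated aim is to determine whether training improves gait speed, and that question needs one named answer.
- **The error rates rest on assumptions.** No passage says that any significant visit will count, or gives an alpha or a correlation. The figures show what an open choice could cost. They are not the trial's error rate, and they do not measure the main defect.

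**Conclusion.** The concern holds in two parts. First, the two-sample tests, the group and group-by-time terms, the ANCOVA treatment effect and the appeal to randomization do not fit the one-group design and cannot yield a treatment effect. This follows from the text alone. Second, the runnable analyses of the 10 Meter Walking Test have three candidate times, no deciding contrast and only a hint of a baseline rule. Under the stated assumptions this could raise the chance of a false improvement from 2.5% to about 5–6.4% at correlations of 0.5 to 0.8, or 3.8–7.3% over 0.95 to 0. That is a modest, conditional figure. The stronger reason to act is that the analysis section does not describe the study in the design sections. It should be corrected before analysis.

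**What to change.** 1. Delete the two-sample, group-factor, ANCOVA and randomization text. If a second group exists, describe it and its allocation instead.
2. Name one primary contrast, for example change in 10 Meter Walking Test speed from the mean of the pre-training measures to discharge. State how a missing pre-training measure is handled.
3. Test it once at two-sided 5%. A paired t-test is enough. A REML mixed model with time as a four-level factor (baseline mean, midpoint, discharge, 3 months), unstructured covariance and no group term gives the same estimate and standard error with complete data, and uses all available data when some are missing.
4. Label the midpoint, 3-month and Wilcoxon results supportive.
5. Reconcile the discharge visit across Visit Schedule, Clinical Outcome Measures, Objective Gait Measures, Statistical Consideration and Schedule of Events. Until then, a contrast that ends at discharge is itself ambiguous.

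The cost is wording and routine software, with no new visits or data. The downside is that significance at midpoint or 3 months alone could no longer support the primary claim.

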The information gained with this study will permit a power analysis so that we can test whether this treatment is more effective than the standard training. The target sample size for this pilot study is 55 patients. We have experienced <5% dropout rate for the treatment, and a 10% drop out rate to complete all measurements, including the 3 month follow up.

DEVICE (ROBOT) INFORMATION

All of the robotic devices that we are proposing to use in patient training trials have been exempt by the FDA. The FDA has ruled that these devices are powered exercise machines. These rulings are provided in the supplementary material. This is also the reason we are filing an expedited review.

Technical Engineering Information

The robot control system is an impedance controller that modulates the way the robot reacts to mechanical perturbation from a patient or clinician and ensures a gentle compliant behavior. Impedance control [24] has been the central contribution of [name]'s engineering research since the early eighties and has been extensively adopted by other robotics researchers concerned with human-machine interaction. At present the MIT-MANUS impedance controller is implemented using coupled nonlinear position and velocity feedback structured to produce a constant isotropic end-point stiffness and damping. High-bandwidth current-controlled amplifiers produce motor output torques directly proportional to commanded input. These facts make the robot a stable device.

For this application, the most important feature of the controller above is that its stability is extremely robust to the uncertainties due to physical contact [25-27] . The stability of most robot controllers is vulnerable when contacting objects with unknown dynamics. In contrast, dynamic interaction with highly variable and poorly characterized objects (to wit, neurologically impaired patients) will not de-stabilize the impedance controller above; even inadvertent contact with points other than the robot end-effector will not de-stabilize the controller. This is essential for safe operation in a clinical context.

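### The planned repeated-measures ANOVA has no rule for incomplete records and, as classically fitted, would drop about 3 to 5.5 of 55 participants who finish training, including from its discharge estimate

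*Combined protocol and SAP*

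**What the plan says.** Under Statistical Consideration and Data Analysis, the schedule is: "The clinical evaluations will be administered at baseline, 9 (midpoint) and 18 (discharge) sessions, and 3 months after completion". The first within-group analysis listed is pairwise: "The paired t-test (and nonparametric Wilcoxon signed-rank test) will be used to evaluate mean score changes for different interventions". A repeated-measures model is then added: "We will also perform a repeated measures analysis of variance (RMANOVA) with group as a between-subject factor, and time as a within-subject factor". The section does not say which time points enter that model, who is analysed, or what happens to a participant with a missing visit. No other section gives a complete-case rule, an imputation method or a mixed model. The only allowance for missed appointments, under Visit Schedule, lets training run to 8 weeks. That does nothing for a missed 3-month visit.

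Under Power Analysis the plan gives the sample size, "The target sample size for this pilot study is 55 patients", and its only attrition figures: "We have experienced <5% dropout rate for the treatment, and a 10% drop out rate to complete all measurements, including the 3 month follow up".

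**The concern.** The two attrition figures differ by at least a factor of two, so on past experience some participants finish training yet lack a measurement. Classical repeated-measures ANOVA needs a value in every within-person cell. A participant seen at discharge but not at 3 months is removed from the whole model, so a discharge speed already collected is not used.

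The paired tests lose people one comparison at a time. The discharge test therefore includes participants whom the 3-month test does not. If those who gained less are the ones who stay away, setting the two results side by side understates how much of the gain is lost. The pilot asks whether gait speed improves and measures it again 3 months after training, and its results are meant to feed the power calculation of a later trial. An inflated gain, or inflated retention, would carry into that calculation.

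**Working it through.** **Inputs from the documents.** N = 55; treatment dropout below 5%; 10% not completing all measurements (all under Power Analysis). The plan gives no alpha, power, effect size or SD behind the 55, so there is no plan calculation to reproduce.

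**Counts.** Assume that everyone who stops treatment also has an incomplete record.
- Complete records: 55 × 0.90 = 49.5.
- Finish training: between 55 × 0.95 = 52.25 (dropout at 5%) and 55 (dropout at 0%).
- Finish training with an incomplete record: 52.25 − 49.5 = 2.75, up to 55 − 49.5 = 5.5.
- Share of finishers lost: 2.75/52.25 = 5.3%, up to 5.5/55 = 10%.

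**Does the method delete them?** A simulated 55 × 4 data set was built in which 3 people had no discharge or 3-month value and 3 more lacked only the 3-month value. A standard repeated-measures ANOVA routine rejected it as unbalanced. After listwise deletion it ran on 49 people, although 52 had a discharge value. A mixed model used all observed visits; its standard error for the discharge change was 0.0200, against 0.0208 in complete cases.

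**Cost if loss is unrelated to response.** Standard error ratio = √(finishers/complete): √(52.25/49.5) = 1.027, up to √(55/49.5) = 1.054.

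**Cost if loss is related to response.** None of these values is in the documents; all are assumptions: mean gains of 0.05, 0.10 and 0.08 m/s at midpoint, discharge and 3 months; SD of change 0.12 m/s; correlation 0.7; log-odds of missing the 3-month visit rising by 1 per SD of smaller discharge gain. The lost participants all have a discharge value.

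| Finishers lost | Discharge gain overstated by | 3-month gain overstated by |
|---|---|---|
| about 5% (about 3 people) | about 0.0055 m/s | about 0.004 m/s |
| 10% (5.5 people) | about 0.011 m/s | about 0.0075 m/s |

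As shares of the assumed gains: 0.0055/0.10 = 5.5% to 0.011/0.10 = 11% at discharge, and 0.004/0.08 = 5% to 0.0075/0.08 = 9.4% at 3 months. For scale, the standard error of a mean change in complete cases is 0.12/√49.5 = 0.017 m/s.

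**Apparent retention from the paired tests.** The assumed true loss from discharge to 3 months is 0.10 − 0.08 = 0.020 m/s. Comparing everyone's discharge change with the attenders' 3-month change gives 0.020 − 0.004 = 0.016 m/s at about 5% lost, and 0.020 − 0.0075 = 0.0125 m/s at 10%. Restricting both visits to attenders errs the other way: 0.020 + 0.011 − 0.0075 = 0.0235 m/s at 10%.

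**Estimate using all observed visits.** In the same simulation the likelihood estimate was biased by no more than about 0.0004 m/s. This follows from the set-up, because missingness was made to depend only on the observed discharge gain.

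**The case against.** The best defence is that the repeated-measures model is an additional analysis, aimed at treatment-by-time interaction. The paired tests come first, and the discharge test retains everyone with a discharge value. This stands. A reader might infer that the trial's discharge result as a whole is biased by later dropout; the plan does not support that, because the problem is confined to the repeated-measures model. The paired tests do not, however, repair the comparison between discharge and 3 months.

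A reader might also infer that the plan prescribes complete-case analysis. It does not: it is silent, and deletion follows from how the method is usually fitted, with all time points in one model. Likewise, a reader might take the rates as the plan's expectation that 10% will miss the 3-month visit. The text reports past experience, and the second rate, "a 10% drop out rate to complete all measurements, including the 3 month follow up", covers any missed measurement. Because the first is only an upper bound, the ratio is two or more, not exactly two.

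Finally, the near-zero bias of the likelihood estimate is a product of the assumed mechanism. If people stay away because of their unobserved 3-month walking speed, a mixed model is biased too. That limits what the remedy can promise, but it does not favour deleting observed data.

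**Conclusion.** The point holds at modest size. With no stated rule, a classically fitted repeated-measures ANOVA would discard about 3 to 5.5 of 55 participants who finished training, along with any discharge speed recorded for them. This assumes that the past rates recur, that all time points enter one model, and that those who stop treatment are among those with incomplete records. The certain cost is precision, a standard error about 3% to 5% larger. Bias arises only if loss is related to response. Under the stated assumptions it is about 0.0055 to 0.011 m/s at discharge and 0.004 to 0.0075 m/s at 3 months, below the standard error of about 0.017 m/s. The upper figures require all 10% to have discharge data, meaning no treatment dropout. The documents do not support a claim that the pilot's conclusions are seriously compromised. They do support changing the model, because a better use of data already collected costs almost nothing.

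**What to change.** Under Statistical Consideration and Data Analysis:
- Replace the repeated-measures ANOVA with a likelihood-based mixed model for repeated measures: visit as a categorical effect, unstructured within-person covariance, and all observed visits of everyone who began training. Take the discharge change, the 3-month change and the difference between them from this model.
- State how the three pre-training measurements form the baseline, for example as the mean of those available.
- Include a group term only once it is settled, as a separate matter, whether the study has two groups.
- Keep the paired t and signed-rank tests as supporting analyses. Report the discharge change both for all participants and for those seen at 3 months, so that any difference between them is visible.
- State that the model assumes data are missing at random, and that it does not remove bias if loss depends on the unobserved 3-month speed.

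The cost is a change of wording and slightly more analysis work. No extra participants, visits or data are needed. Settling this before the data are analysed also avoids choosing the missing-data handling after results are seen.
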